**Precis**

Prior studies (92-CH-0011) have been important in establishing synthetic human parathyroid hormone 1-34 (PTH) as a beneficial treatment for hypoparathyroidism, superior to conventional therapy with calcitriol and calcium supplements. The simultaneous normalization of serum and urine calcium, phosphorus, magnesium and markers of bone turnover remains the main goal of this hormone replacement therapy. Abnormalities in mineral homeostasis, characteristic of hypoparathyroidism, are not remedied with conventional therapy and remain problematic with both once and twice daily PTH injection therapy. Further refinement and physiologic control of calcium metabolism in PTH replacement therapy of hypoparathyroidism are needed. We will be conducting a short-term, inpatient-outpatient study of 24 subjects in a randomized crossover study comparing twice-daily subcutaneous injections vs. PTH pump therapy. We hypothesize that PTH pump therapy will provide smoother metabolic control of serum mineral levels and normalization of urine mineral excretion compared to a twice-daily regimen. The protocol design includes three inpatient admissions: baseline, 3 months, and 6 months. There will be two study arms (PTH delivery by pump vs twice daily subcutaneous injections; each arm divided into an inpatient and an outpatient phase. Subjects will be randomized to either pump therapy or to twice daily injections at the beginning of the study and will cross over to the alternate PTH delivery system (injections vs. pump) at the conclusion of the initial 3-month (13 weeks) treatment period. A central goal of the study is to gain experience with the use of PTH pump therapy as an alternative to multiple daily injections and to establish safety and efficacy. Although the pump is widely used in type 1 diabetes for delivery of insulin, this delivery system has never been applied to PTH therapy for hypoparathyroidism. This study will test the ability of the insulin pump (omnipod) to maintain normal mineral levels and to confirm the device does not adversely impact calcemic control or patient compliance. Additionally, the study will demonstrate whether PTH delivered by pump is sufficiently well tolerated to expect adherence will be satisfactory.

## 45     **PROTOCOL**

### 46     **Background and Scientific Justification**

47     Hypoparathyroidism is a rare condition resulting in abnormalities in mineral metabolism. Hypocalcemia leads  
48     to neuromuscular irritability causing tetany, cramping, carpal pedal spasms, and seizures. Conventional  
49     therapy with vitamin D analogs increases intestinal calcium absorption, which increases serum calcium levels  
50     but does not correct the lack of renal calcium reabsorption that is typical of this disorder. Normalization of  
51     serum calcium levels with conventional therapy is often accompanied by abnormally high levels of urine  
52     calcium. Chronic hypercalciuria, a frequent consequence of conventional therapy, may lead to  
53     nephrocalcinosis, renal insufficiency or failure (1-11). Iatrogenic hypercalciuria, the result of the interplay of  
54     therapeutic intervention to normalize serum calcium levels and compromised physiological defenses against  
55     rising urine calcium concentrations, is the limiting factor in the management of hypoparathyroidism. The  
56     attempt to normalize serum calcium levels causes a vicious cycle of recurrent hypercalciuria which leads to  
57     permanent renal damage. This causes significant morbidity in most patients, and eventually leads to renal  
58     insufficiency and, in some cases, renal failure. This possibility precludes the maintenance of eucalcemia over a  
59     lifetime of hypoparathyroidism and thus full realization of the long-term benefits of adequate calcemic control.  
60     Thus, most patients suffer from chronic symptoms associated with hypocalcemia, which is required to avoid  
61     renal damage. The Vitamin D analogs remain the only FDA approved and generally available treatment.  
62     Chronic hypoparathyroidism is one of the few remaining hormonal insufficiency states for which replacement  
63     with the missing hormone is unavailable. PTH injections have enabled, for the first time, simultaneous  
64     normalization of serum and urine calcium. Further refinement is possible as serum magnesium and phosphorus  
65     and bone turnover markers remain abnormal in many patients. Additionally, there are transient episodes of  
66     hyper and hypocalcemia intermittently through the day with both once and twice daily injections. Therefore,  
67     twice daily PTH has been shown to improve urine calcium excretion with overall simultaneous normalization  
68     of serum calcium, this method of delivery of the drug is not yet entirely physiologic.

69     PTH replacement therapy in hypoparathyroidism has been studied in three prior clinical trials (92-  
70     CH-0011). The initial pilot study of 10 patients (12) demonstrated that PTH maintained both serum and  
71     urinary calcium in the normal range over a 24-hour period when given as a daily subcutaneous injection. PTH  
72     resulted in a lower urinary calcium level than calcitriol for a given level of serum calcium and maintained  
73     serum calcium within the normal range as well or better than calcitriol. Fluctuations of serum calcium within  
74     the normal range were produced in response to PTH injections. Subsequently, results of a randomized  
75     controlled dose study (13) showed that twice-daily, compared to once daily, PTH provides effective short-  
76     term treatment for hypoparathyroidism with a markedly reduced total daily dose, an apparent reduction in bone  
77     turnover, and a decreased incidence of bone pain compared to a once-daily regimen. Twice-daily PTH  
78     produced higher levels of serum calcium, with fewer fluctuations into the hyper and hypocalcemic range.  
79     Markers of bone turnover were elevated above the normal range in response to both treatment regimens,  
80     however, twice daily produced significantly lower serum marker levels suggesting that this dose regimen  
81     increased bone turnover to a lesser extent than once daily PTH. Furthermore, serum phosphorus levels remain  
82     elevated during PTH injection therapy. In the third study, 27 adults with hypoparathyroidism were  
83     randomized to either calcitriol or PTH (14). Our findings demonstrate that twice-daily PTH administration  
84     maintains serum calcium in the low normal or just below the normal range over a 3-year period with  
85     concurrent normalization of urinary calcium excretion. In the PTH treated group, however, serum phosphorus  
86     remained elevated and markers of bone turnover (osteocalcin, alkaline phosphatase) were significantly  
87     elevated during the three-year study, at levels at least two-fold greater than normal. Despite this increase in  
88     bone turnover, there was no change in the BMD as measured with dual energy x-ray absorptiometry (DXA).  
89     Thus, it follows that, all other factors being equal, reducing the calcemic fluctuation and eliminating transient  
90     episodes of hypercalcemia will also reduce hypercalciuria. Furthermore, it follows from the pathophysiology,  
91     that these improvements in the calcemic profile will ultimately be more physiologic for the kidney and bone.

### 93     **Objectives**

94     The primary objective of this pilot study will be to evaluate the safety, biological activity and  
95     pharmacodynamics of PTH 1-34 comparing delivery by twice daily subcutaneous injection vs. an insulin pump.  
96     The levels of serum calcium, phosphorus, magnesium, 1,25 OH vitamin D, bone markers, and mineral levels  
97     and cyclic AMP in the urine are the key physiologic responses to determine the adequacy of the PTH effect on  
98     hypoparathyroidism. We hypothesize that the delivery of PTH via pump therapy will maintain serum calcium  
99     in the normal range with minimal or no fluctuations in blood mineral levels. We anticipate that the small  
100     increments of PTH released by the pump will result in a normal physiologic pharmacodynamic profile of

serum calcium, magnesium, phosphorus and 1,25 vitamin D, normalize urine calcium and cause mild increases in urinary phosphorus and cAMP with no apparent peaks or troughs throughout the day.

This protocol is being conducted to study PTH delivered via pump vs. twice daily subcutaneous injections. PTH therapy via pump or twice-daily subcutaneous injections will be compared in a randomized crossover study consisting of two 3-month treatment arms.

The specific hypotheses and study endpoints are as follows:

We hypothesize that PTH pump therapy will be better tolerated, more convenient, and the preferred treatment modality. We expect that pump delivery of PTH will provide smoother metabolic control of serum and urine mineral levels compared to twice-daily injections. Our premise is that pump delivery will produce a more physiologic delivery of PTH by reducing brief episodes of hyper- and hypocalcemia throughout the day, will

permit improved calcemic control in the blood and will be more physiologic to the bone and kidney, with normal bone markers and reduced urine calcium.

The primary objective of this pilot study will be to evaluate the safety, efficacy, and pharmacodynamics of PTH1-34 given as twice-daily subcutaneous injection compared to an insulin pump. The levels of serum calcium, phosphorus, magnesium in the blood and urine are the key physiologic responses to determine the adequacy of the PTH effect on hypoparathyroidism. We hypothesize that the delivery of PTH via pump therapy will maintain serum calcium in the normal range with minimal or no fluctuations in blood mineral levels.

We expect that occasional or no episodes of hypo or hypercalcemia will occur during both daily (pre-dose lab testing) or 24 h testing periods. Furthermore, there will be no diminishing effects of the pump's ability to maintain normal mineral homeostasis over the 3-month period.

Secondary objectives are:

Secondary objectives include measuring serum 1,25 OH vitamin D and cyclic AMP in the urine.

Biochemical marker of bone health: markers of bone formation and resorption in the blood and urine.

To determine if PTH therapy provides significant relief to patients with hypoparathyroidism who generally complain of debilitating fatigue, muscle weakness and decreased endurance. Fatigue scale questionnaire, a self measure of impact of fatigue (15) on activity and 6-minute walk-run test, a test of cardiovascular fitness and functional capability, in accordance with the guidelines and methods described and established by the American Thoracic Society (16,17). A biodex test of muscle endurance will also be performed. These tests will be administered in the Rehabilitation Medicine Department. These measures may help determine if PTH provides significant improvement of these symptoms. This section of the protocol will be performed by the Rehab Medicine collaborators.

**Study Design/Sample Size:** Study including 24 subjects with chronic hypoparathyroidism comparing PTH pump delivery vs twice daily PTH 1-34 injections.

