### **Summary of Protocol**

Patients with hypoparathyroidism who meet the inclusion criteria will be admitted to the Clinical Center for an initial inpatient dose-adjustment phase lasting 7-10 days. PTH therapy (via pump) or twice daily subcutaneous injections will be compared in a randomized crossover study consisting of two 3-month treatment arms.

Randomization to either twice-daily or pump PTH therapy will take place at the beginning of the first admission. The initial admission will consist of daily urine and blood collections for mineral levels to determine the best dose of PTH. During the pump arm only, toward the end of the initial dose adjustment phase (day7), there will be a 24h test of serial blood collections to further determine if the dose of PTH is adequate. Patients will be discharged and followed on an outpatient basis for 3 months. During this period, weekly serum and urine mineral levels will be measured. After 3 months, patients will be re-admitted to the Clinical Center. At the beginning of this admission, a 24-h serial test will be performed to measure serum and urine minerals, serum vitamin D and urine cyclic AMP levels. The patients will then cross over to the opposite treatment arm and will undergo the identical measures for the second 3-month treatment arm. The third and final admission will last 3-5 days. At the conclusion of the study, patients will be discharged to their local physicians for care of their hypoparathyroidism. Investigational drug preparation and randomization will be carried out by the NIH Clinical Center Pharmaceutical Development Service. At baseline, 3 months, and 6

months, subjects will undergo evaluation in the Rehabilitation Medicine department for evidence of muscle weakness, decreased stamina and fatigue. This is an important part of the study as we hypothesize PTH therapy will provide a substantial improvement.

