## Monitoring of Subjects

*Baseline (Admission 1):* Admissions will include height, weight, general medical history, urine pregnancy and a physical exam. Additionally, routine hematological evaluation (CBC), hepatic function studies, mineral panel, alkaline phosphatase, thyroid functions, vitamin D, intact PTH. Daily AM fasting blood: acute care and mineral panels, every other day (x 3 collections) blood and urine collections for bone markers: serum osteocalcin, bone specific alkaline phosphatase, 24-hour urine pyridinium crosslinks. Daily 24-hour urine collections will be obtained for measurement of calcium, phosphate, magnesium, and creatinine clearance. Patients will fill out a symptom questionnaire to determine their symptoms related to hyper- or hypocalcaemia. At the 3-month and 6-month time points, the response to therapy will be compared and examined over a 24-h period with every 2 h measures of mineral levels in the serum and every 4 h measures in the urine. Fatigue scale questionnaire (Self measure of impact of fatigue on activity) and 6-minute walk-run test, and a Biodex test for muscle endurance will be administered in the Rehabilitation Medicine Department at baseline, 3, and 6-month time points.

1. The Clinical center admission 1 and 2 will last approximately 10-12 days and include the following:

- Monitoring of effects of PTH with q12 hr serum calcium levels: Twice daily blood calcium levels may be performed during the initial days of pump therapy monitoring to identify the optimal basal rate. The PI will determine the need for serum calcium levels at this frequency.
- If a subject reports symptoms of hypocalcemia, the blood calcium will be checked. When the blood calcium is  $<1.7$  mmol/L mg/dL, the subject will receive treatment for hypocalcemia by increasing the dose, providing calcium carbonate (600 mg calcium PO) or with 1 cup of calcium fortified orange juice. Additional calcium measurements will be made as needed until the blood calcium is  $>1.8$  mmol/L
- Subcutaneous injection or pump teaching
- Assessment of the baseline pre-PTH measures of fatigue endurance and muscle strength and endurance.

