## Medications

*Treatment with PTH:* Subjects will be randomized at the beginning of the first inpatient admission and will remain on this dose schedule until the second admission (3 months later). Synthetic human parathyroid hormone 1-34 will begin on day 3 of the first admission and will be given as a twice daily subcutaneous injection as a divided dose at 0800 h and 2000 h or via a pump. PTH is prepared by the Clinical Center PDS in two vial strengths: 50 mcg/mL and 200 mcg/mL. The initial PTH dose will be 0.5 µg/kg/day for twice daily dosing and 0.2 µg/kg/day for pump therapy. The total daily dose will be adjusted by approximately twenty percent increments for mild hypo- or hypercalcemia. For severe hypocalcemia, the dose will be adjusted by larger increments and calcium supplements may be added. For severe hypercalcemia, the patient will stop the drug for at least one day and then resume treatment at a lower dose. For further details of pump therapy, see appendix 2

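### No urinary cAMP assay is listed before PTH starts, so the predicted mild rise cannot be estimated as a change from the pre-PTH level

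*Combined protocol and SAP*

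**What the plan says.** The Objectives section gives urinary cAMP two roles. The opening statement of the primary objective lists serum minerals, 1,25 vitamin D, bone markers and urine minerals, and ends with "cyclic AMP in the urine are the key physiologic responses to determine the adequacy of the PTH effect on" hypoparathyroidism. It then anticipates that the pump will "cause mild increases in urinary phosphorus and cAMP with no apparent peaks or troughs throughout the day". The secondary objectives later state: "Secondary objectives include measuring serum 1,25 OH vitamin D and cyclic AMP in the urine". No reference level for the increase is named.

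The Medications section fixes the start of treatment: "Synthetic human parathyroid hormone 1-34 will begin on day 3 of the first admission".

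For the first admission, Monitoring of Subjects states: "Daily 24-hour urine collections will be obtained for measurement of calcium, phosphate, magnesium, and creatinine clearance". The bone markers listed with it are "serum osteocalcin, bone specific alkaline phosphatase, 24-hour urine pyridinium crosslinks". Neither list contains cAMP.

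The Summary of Protocol schedules urinary cAMP at the 3-month admission, where "a 24-h serial test will be performed to measure serum and urine minerals, serum vitamin D and urine cyclic AMP levels". It continues: "The patients will then cross over to the opposite treatment arm and will undergo the identical measures for the second 3-month treatment arm". Monitoring of Subjects sets urine collection during these tests at every 4 hours.

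**The concern.** To say that a treatment causes an increase, one needs a level without the treatment. For cAMP, both planned measurements are taken after about three months or more on PTH, one on each delivery method. They can show whether the methods differ from each other. They cannot show how far either moved cAMP from where the subject began, or whether that movement was mild.

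What is at stake is one stated prediction about a response that the plan calls key, for a delivery route that the Precis says has never been applied to PTH in this disease. It looks like an omission. Urinary phosphorus, the other half of the same prediction, is assayed in the baseline urines, and the plan also schedules pre-PTH measures of fatigue, strength and endurance.

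**Working it through.** The plan gives no figure for this point, so there is none to reproduce. The check sets every scheduled urine measurement against the start of PTH on day 3.

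| Scheduled measurement | Section | On PTH? | Urine cAMP listed? |
|---|---|---|---|
| Admission 1, daily 24-h urine, days 1-2 | Monitoring of Subjects | No | No (calcium, phosphate, magnesium, creatinine clearance) |
| Admission 1, daily 24-h urine, day 3 on | Monitoring of Subjects | Yes | No |
| Admission 1, urine bone markers, three alternate-day collections | Monitoring of Subjects | Depends on day | No (pyridinium crosslinks) |
| Day-7 test, pump arm only | Summary of Protocol; Monitoring of Subjects | Yes | No (blood only) |
| Outpatient urine | Summary of Protocol; Monitoring of Subjects | Yes | No (minerals, bone markers) |
| 24-h test at 3 months | Summary of Protocol | Yes | Yes |
| 24-h test at 6 months | Summary of Protocol | Yes | Yes (identical measures) |

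**Counts.** Scheduled cAMP occasions before PTH: 0 per subject, so 0 of 24. On PTH: 2 per subject, one per delivery method. No washout is described at crossover, so no off-treatment value arises later.

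**What can be estimated.** Let P and I be a subject's cAMP on pump and on injections, and B the value before PTH.
- P − I: estimable within subject from the 3- and 6-month tests.
- The 24-hour profile on each method: estimable from 24 h ÷ 4 h = 6 urine fractions per test.
- P − B and I − B: not estimable, because B is not assayed.

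**What already exists.** With PTH starting on day 3, days 1 and 2 give up to 2 PTH-free 24-hour collections per subject. That is 24 × 1 = 24 collections if one is used and 24 × 2 = 48 if both are. The upper figure assumes that collection begins on day 1 and that consent, which is signed at this admission, does not delay it.

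**Could another passage supply B?** The statement that the second admission mirrors the first does not imply a baseline cAMP test, because Monitoring of Subjects places the 24-hour comparison at 3 and 6 months. Appendix 2 (pump details) is cited under Medications but is not in the text available, so it could not be checked.

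**The case against.** The strongest reply is that the plan's comparison is pump against injection within subject, and the scheduled cAMP data support it. The predictive sentence names no pre-PTH comparator and is partly about the shape of the day, which the 4-hourly fractions address. The restated primary objective drops cAMP, and the secondary objective speaks only of measuring it. The study calls itself a pilot, the sample size rests on serum calcium, and no decision depends on a cAMP change. All of this stands, and it limits the weight of the point. It does not supply a reference for the predicted increase. A laboratory range might serve, but none is named, and a value inside a range does not show a rise from the subject's own starting level.

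A reader might go further and infer that, if pump and injection gave similar cAMP, the trial could not tell whether both regimens act on the kidney or neither does. The documents do not support that. Injections are given at 0800 h and 2000 h, so each 12-hour interval holds 12 ÷ 4 = 3 urine fractions. A rise after an injection relative to later fractions would be evidence of renal stimulation on that method. For the pump, where a flat profile is expected, the inference is less direct, but urinary phosphorus and urine calcium have pre-PTH assays and also bear on renal effect.

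A second tempting inference is that the samples themselves are lacking. They are not: the urine is collected and only the assay is unlisted.

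There is also a fair caution about any before-after contrast. It would not be randomised. The fixed diet is provided only on the 24-hour test days. The documents do not say when conventional therapy stops, so days 1 and 2 may not represent an untreated state.

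**Conclusion.** The point holds in a limited form. Under the listed measurements, 0 of 24 subjects have a pre-PTH urinary cAMP value, so the change from the pre-PTH level cannot be estimated for pump or for injections. The randomised pump-versus-injection difference in cAMP and the 24-hour profiles are unaffected, as is everything that rests on serum calcium.

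This depends on reading the analyte lists as complete, on the missing Appendix 2 not adding a baseline cAMP assay, and on taking the predicted increase to mean an increase over the level before PTH. The absence of the assay is clear from the text; its consequence is confined to one secondary prediction. The change is worth making because it is cheap and can only be made before each subject's first dose.

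**What to change.** 1. In Monitoring of Subjects, Baseline (Admission 1), add cAMP to the assays on the 24-hour urine already collected before the first PTH dose. Require at least one complete collection, taken after consent.
2. Use one unit at all three time points. Either use total cAMP per 24 hours, which at 3 and 6 months is the sum of the six 4-hour fractions, or use cAMP per creatinine. The second option needs creatinine assayed on the 4-hour fractions, where it is not currently listed. A per-creatinine baseline must not be subtracted from a 24-hour total.
3. Report the change from the pre-PTH value on each delivery method as a descriptive, non-randomised secondary result, beside the randomised pump-versus-injection comparison. State that the fixed diet applies only to the 24-hour test days and that the pre-PTH value may reflect conventional therapy.

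The cost is about 24 to 48 cAMP assays (one or two per subject), creatinine on the 4-hour fractions if the ratio is chosen, and a short protocol edit. No new visit or collection is needed. The baseline urine must be handled in a way suitable for cAMP; the documents are silent on specimen handling, so the laboratory should confirm this.

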### **Enrollment and Baseline Data Collection**

Potential subjects will be evaluated for study eligibility through the evaluation of their medical history, lab data and performance of a physical examination by a study investigator.

*Informed consent:* Prior to their admission, eligible subjects will be invited to participate in the study, and the study procedures will be initially discussed over the phone. At their first inpatient admission, eligible adult subjects will be given a consent form to read and, after discussion with the investigators, if they agree to participate, the consent form will be signed. The consent will be discussed with each subject at a level they can understand. Written informed consent must be obtained prior to performing any study-specific procedures that are not part of the subject's routine care.

Prior to obtaining protocol consent, screening labs will be obtained on subjects to determine protocol eligibility. The NIH general admission consent form (NIH-1225-1) will serve to obtain the patient's consent to obtaining this laboratory evaluation.

*Patient evaluations:* There will be three inpatient admissions at baseline, 3 and 6 months in the NIH Clinical Center. Patients with hypoparathyroidism who meet the above criteria will be admitted to the Clinical Center for an initial baseline inpatient evaluation, patients will be randomized to initially receive one of two possible replacement PTH1-34 regimens: (a) given subcutaneously twice daily or (b) pump therapy. PTH therapy will be initiated. and dose-adjustment will proceed to optimize doses and to maintain normal levels of serum calcium, phosphorus and magnesium and to reduce urine calcium levels. After discharge, patients will be followed on an outpatient basis in collaboration with a local physician and lab. Crossover to the other treatment arm occurs at the second inpatient admission.

*Rehabilitation Medicine:* Patients will be seen in Rehabilitation Medicine at baseline, 3 months, and 6 months. Fatigue scale questionnaire, a self measure of impact of fatigue on activity and 6-minute walk-run test, a test of cardiovascular fitness and functional capability, in accordance with the guidelines and methods described and established by the American Thoracic Society. A biodex test of muscle endurance will also be performed. These tests will be administered in the Rehabilitation Medicine Department.

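### The stated hypothesis that the pump is more convenient and preferred has no planned measurement behind it, and the compliance aim has no systematic adherence measure in the text available

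*Combined protocol and SAP*

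**What the plan says.** The Objectives section opens a list with "The specific hypotheses and study endpoints are as follows". Its first item is "We hypothesize that PTH pump therapy will be better tolerated, more convenient, and the preferred treatment modality".

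The Precis adds two related statements. The study is to test the pump's ability to hold mineral levels and "to confirm the device does not adversely impact calcemic control or patient compliance". It also says "the study will demonstrate whether PTH delivered by pump is sufficiently well tolerated to expect adherence will be satisfactory".

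The secondary objectives are laboratory measures ("Secondary objectives include measuring serum 1,25 OH vitamin D and cyclic AMP in the urine"), bone markers, and tests of fatigue, walking and muscle endurance. The patient-reported instruments are the fatigue scale (Enrollment and Baseline Data Collection: "Fatigue scale questionnaire, a self measure of impact of fatigue on activity and 6-minute walk-run test") and a calcium-symptom form (Monitoring of Subjects: "Patients will fill out a symptom questionnaire to determine their symptoms related to hyper- or hypocalcaemia"). Monitoring of Subjects also has side effects and adverse events solicited at every phone contact and at 6 months.

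The Medications section refers to Appendix 2 for pump details. The text available contains only Appendix 1, the serious adverse event form.

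**The concern.** Preference and convenience are not background remarks here. They sit under the heading for hypotheses and endpoints, and compliance is a stated aim of the Precis. Each needs an observation that can be analysed.

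The design suits the preference question well: every completer uses both methods for about 3 months each, so each can compare them directly. If the question is not asked, any statement in the report that the pump was preferred or more convenient would rest on impression.

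Compliance matters for a second reason. If doses are missed more often on one method, the mineral comparison mixes the effect of the delivery method with the effect of missed drug. Mineral levels cannot separate the two, because the dose is adjusted in response to those same levels.

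**Working it through.** This is mainly a check of aims against assessments. The plan gives no figure for preference, convenience or adherence to reproduce; its only power statement concerns serum calcium at 6 h.

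**Aims against data sources**

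| Stated hypothesis or aim | Where stated | Data source listed |
|---|---|---|
| Better tolerated | Objectives | Yes: side effects and adverse events solicited by phone and at 6 months |
| More convenient | Objectives | None |
| Preferred | Objectives | None |
| No adverse effect on compliance | Precis | No systematic measure |
| Tolerated well enough to expect adherence | Precis | Tolerability as above; adherence is inferred from it |

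**Assessments searched** (Objectives, Summary of Protocol, Enrollment and Baseline Data Collection, Monitoring of Subjects): serum and urine minerals, 1,25 vitamin D, urine cyclic AMP, bone markers, 24-h serial tests, fatigue scale, 6-minute walk-run, Biodex, calcium-symptom questionnaire, solicited adverse events. None asks which method the subject would choose or how convenient it was. No dose log, vial or pod count, or pump download is listed. No analysis of preference, convenience or adherence is described.

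**Precision if the preference question is added**

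Inputs from Sample Size Justification: 24 subjects in total, made up of 8 adults and 16 children. Assume that all complete and answer. The widest approximate 95% half-width is at p = 0.5:

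half-width = 1.96 × √(0.25/n)

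- n = 24: 1.96 × √(0.25/24) = 0.200, about ±20 points
- n = 16: 1.96 × √(0.25/16) = 0.245, about ±25 points
- n = 8: 1.96 × √(0.25/8) = 0.346, about ±35 points

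With so few subjects the report should use exact (Clopper-Pearson) limits. If 75% preferred the pump, for illustration:

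- 18 of 24: 53.3% to 90.2%
- 6 of 8 adults: 34.9% to 96.8%

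So 24 answers could show a clear preference, while the adult stratum alone would be descriptive.

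**The case against.** The strongest objection is about rank. This is a pilot whose primary objectives are safety, efficacy and pharmacodynamics, and whose secondary objectives are laboratory, fatigue and function measures. Preference, convenience and adherence are in neither list, and the results for those lists do not depend on preference or convenience data. That stands, and it limits the weight of the point. It does not remove it, because preference and convenience are still listed under the specific hypotheses and endpoints.

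On adherence, three stronger readings are tempting, and the documents do not support them.

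- A reader might infer that the Precis promises to demonstrate adherence. The sentence in question ("the study will demonstrate whether PTH delivered by pump is sufficiently well tolerated to expect adherence will be satisfactory") measures tolerability and reasons from it to expected adherence. Only the separate compliance clause is a direct aim.
- A reader might infer that no dosing record exists at all. That cannot be asserted while Appendix 2 is unseen. What can be said is that none is listed in the text available, and that a pump record would give nothing on injections.
- A reader might infer that there would be no compliance information whatever. Subjects are phoned about every 3 days for 3 weeks and then weekly. The Protocol Stopping Criteria also require staff to notice persistent handling errors with the pump and with vials, and to judge whether a severe event reflects noncompliance. That is some information for both methods, but it is unsystematic and no analysis is attached to it.

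A reader might also infer that preference could never be recovered. A call is scheduled about 4 days after final discharge, when completers have used both methods, so it could still be asked then. The plan does not provide for this. Dose-level adherence is much harder to reconstruct.

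**Conclusion.** The point holds mainly for preference and convenience. They are stated as part of a specific hypothesis, and no listed assessment records them, so the plan as written supplies no planned data to test that part. Tolerability is covered.

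Compliance is a second, more qualified point: it is a stated aim with no systematic measure listed for either method, subject to what Appendix 2 contains.

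One added preference question would give an estimate to about ±20 points overall and about ±35 points in the 8 adults. These figures assume that all 24 subjects complete and answer; dropout widens them. The overall figure also pools post-surgical adults with children who have more severe disease, and eligibility starts at age 7, so the strata should be shown separately and the respondent defined. The primary mineral comparisons remain answerable, so this is an improvement that should be made, not a fatal flaw.

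**What to change.** **Preference and convenience.** At the existing 3- and 6-month admissions, add a short convenience rating of the method just used. At 6 months, add one forced-choice preference question, completed before results are discussed with the subject. State whether the child or the parent answers for young children. Report the proportion preferring the pump with an exact 95% confidence interval, overall and separately for adults and children. Compare the convenience ratings within subject.

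**Compliance.** Ask about missed or interrupted dosing at the scheduled phone calls in both periods. Keep a dated record of the prescribed dose: doses change during follow-up and the drug comes in two vial strengths, so returned vials alone would not show what was taken. Choose one metric that applies to both methods, such as percent of prescribed daily dose delivered or percent of days with full dosing, and compare it within subject with a 95% confidence interval. If Appendix 2 already describes a pump record, cite it and add the injection counterpart.

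**Alternative.** Remove the preference, convenience and compliance claims from the stated hypotheses and aims.

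**Cost.** A one-page form at visits already planned, an extra question at calls already scheduled, and upkeep of the dose record. Subject burden rises slightly. Answers remain subjective because the subject knows which method was used.
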